PROTOCOL TITLE: Neonatal Esophagus and Airway Interactions in Health and Disease: Mechanisms and Management of Infant Dysphagia

PROTOCOL TITLE:

Neonatal Esophagus and Airway Interactions in Health and Disease: Mechanisms and Management of Infant Dysphagia

PRINCIPAL INVESTIGATOR:

Name: [name]

Department/Center: Neonatal and Infant Feeding Disorders Program/Center for Perinatal Research

[contact]

Email Address: [contact]

VERSION NUMBER/DATE:

Version 10(revision #9) 10/2/20

REVISION HISTORY

Revision #	Version Date	Summary of Changes	Consent Change?
1	12/21/15	During the intervention phase while thickened formula is in use, we changed the definition of compliance from < or equal to 75% of the time to < or equal to 50% of the time	No
2	1/12/16	Allowed less percentage of PO intake at time of screening to account for provider led restrictions vs. infant led restrictions	No
3	2/26/16	
1. Allowed subjects on acid suppressive therapies at the time of VFSS into our recruitment as well as allow oatmeal as a second option for thickening.2. Added the addition of video use during manometry in our methods section. Concurrent synchronized video recordings will be performed to further validate symptoms based on objective definition of the esophageal reflexes.3. Documentation of symptom markers can be validated by integrating manometry with respiratory inductance plethysmography and video.4. Updates to the PHI page and privacy section of the consent to state the infant's face will be in view of the video.4. Updated DSMB members.	Yes
4	4/24/17	Changed reimbursement language to reflect use of ClinCard	Yes

PROTOCOL TITLE: Neonatal Esophagus and Airway Interactions in Health and Disease: Mechanisms and Management of Infant Dysphagia

5	6/12/17	At inception, the protocol was written as a randomized control trial comparing two different feeding approaches: flow regulation vs. thickened feeds. However, over the period, we found it difficult to recruit and retain subjects. Based on the recommendations of the DSMB and program project team, we addressed the hypotheses using alternative strategies. One of such strategies is reflected in this amendment, wherein, the proposed change instead of the interventions being randomly assigned, parents will now choose which therapeutic feeding strategy they would like to enroll their infant in. This is called the parent-preferred feeding therapeutic strategy.	Yes
6	10/18/17	Replaced redlined version of protocol with clean version	Yes
7	2/8/18	A detailed review of the protocol as written revealed multiple changes in study team members and data collection methods that had not been addressed in the body of the protocol. Although the focus and outcome measures of the study have not changed, the protocol was amended to reflect the updates suggested by the DSMB.	Yes
8	1/4/19	Updates to statistical analysis and sample size as well as updated protocol to new template	Yes for new IRB requirements
9	10/2/20	Clarification and summary of changes to the protocol thus far have been made for improved readability, reproducibility and clarity for the reader as this needs to be submitted along with the manuscript.	No

1.0 Study Summary

Study Title	Neonatal Esophagus and Airway Interactions in Health and Disease: Mechanisms and Management of Infant Dysphagia
Study Design	Single arm observational study
Primary Objective	Our overall aims are to identify novel diagnostic aerodigestive targets, define effective therapeutic interventions, and advance the mechanistic basis of therapeutic outcomes-i.e., full oral feedings.
Secondary Objective(s)	
 1) Examine the differences in outcomes among preterm born vs. full term born 2) Examine the differences in outcomes among those with normal versus abnormal VFSS
Research Intervention(s)/Investigational Agent(s)	Providing esophageal manometry concurrent with video fluoroscopy swallow study (VFSS) in order to determine sensory-motor dysphagic mechanisms which will better inform treatment options
IND/IDE #	N/A

PROTOCOL TITLE: Neonatal Esophagus and Airway Interactions in Health and Disease: Mechanisms and Management of Infant Dysphagia

Study Population	
All infants will have a diagnostic VFSS scheduled.
 
Inclusions: Infants with feeding-related aerodigestive symptoms who are \leq 60 weeks PMA (both pre-term and full-term) who are orally feeding $\geq 25\%$ of at least 50% of their feeds who are on full enteral feeds with no more than 1LPM NC respiratory support.
 
Exclusions: Genetic or metabolic syndromes, IVH grade III or greater, moderate to severe HIE, craniofacial, airway or foregut malformations or ENT or neuro surgeries. Infants who are exclusively breastfeeding are also excluded.

Sample Size	60
Study Duration for individual participants	Up to 4 weeks (initial manometry study with diagnostic VFSS, repeat manometry at 4-6 weeks as relevant), will follow feeding outcomes and growth and developmental outcomes for 1 year
Study Specific Abbreviations/ Definitions	
VFSS video-fluoroscopy swallow study
 
LP laryngeal penetration
 
LA laryngeal aspiration

2.0 Objectives

2.1 Purpose, Specific Aims or Objectives

- Our overall aims are to identify novel diagnostic aerodigestive targets, define effective therapeutic interventions, and advance the mechanistic basis of therapeutic outcomes. Infants with aerodigestive and feeding difficulties, who had VFSS undergo Manometry study to ascertain the mechanisms of normal or abnormal swallowing. Parent-preferred therapy is implemented. Changes in therapy modes are documented. Repeat manometry study is undertaken at time-2, which is 2-4 weeks after the initial study where feasible (this may happen in those with oral feeding failures).
- Based on the VFSS results evaluations, there are 2 possible scenarios: those with abnormal or normal results. Parent preferred therapeutic feeding (flow change, thickener change, no change) strategy is implemented and we will simply monitor the progress of the feeding efficiency till discharge or four weeks, whichever is earlier. There are 2 possible outcomes: feeding success, i.e., full oral feeds without symptom requiring intervention or feeding failure, i.e., those needing any tube feeding.
- We will review the motility characteristics of the successful and failure cases to identify the diagnostic markers.

2.2 Hypothesis

- The central unifying hypothesis supported by our preliminary data is that VFSS with the addition of Manometry along with parent preferred feeding strategy is more effective in preventing long term feeding tubes in infants with aerodigestive problems and feeding difficulties.
- **Primary Hypothesis:** The addition of manometry for diagnostics and parent preferred therapy for management is more effective than VFSS with provider recommendations alone for achieving primary outcome.
- **Secondary Hypotheses:** 1) The sensory- motor characteristics of pharyngo-esophageal motility markers are distinctive between normal and abnormal VFSS results. 2) Clinical outcomes are distinct with flow modification and thickener use.

3.0 .Background

3.1 Relevant prior experience and gaps in current knowledge.

- Dysphagia or abnormalities of swallowing, is a heterogeneous condition of multiple etiologies. Pharyngeal phase is the most critical phase since imprecise regulation is associated with airway consequences such as laryngeal penetration and airway aspiration. Exact prevalence is not known, but is estimated to be about 30% to 60% among neonatal ICU graduates. Although these numbers highlight the economic burden, they ignore the quality of life for both patients and parents. The lack of a pathophysiology guided diagnostic and safe feeding management strategies continue to be critical barriers to progress in this field. The current proposal focuses on the dynamic changes in the integrative physiology of the neonatal pharynx, upper esophageal sphincter (UES), lower esophageal sphincter (LES) and esophagus during swallowing and GERD; all of which are potential therapeutic targets for neonates with dysphagia. Current treatment approaches in dysphagic infants are likely to fail due to unclear therapeutic targets. Such high risk infants also suffer chronic morbidity, longer hospitalizations, re-admissions, and account for an unacceptable health care burden. Designing effective symptom-based management is very difficult.

3.2 Relevant preliminary data.

PROTOCOL TITLE: Neonatal Esophagus and Airway Interactions in Health and Disease: Mechanisms and Management of Infant Dysphagia

- Three references are attached below in this section that lend support to our investigations, difficulties with strict protocols and need for personalization and parent preferred pragmatic therapies. Complimentary protocols (feeding outcomes in dysphagia, mechanisms of dysphagia, outcomes in gastrostomy bound infants) will address the original study aims as well. Updated statistical procedures based on the advice of our statistician, [name], PhD, DSMB team, and our Program Project Group is shown below.

3.3 Updated statistical procedures:

- The design of the Patient Preferred Trial has been modified to a single arm observational study with patients who have not achieved PO at the time of study or PO with feeding difficulties, comparing VFSS and manometry vs VFSS only (the historical control) on feeding outcomes. The primary outcome is success rate at discharge. We will prospectively follow 60 infants who are not fully PO or PO and symptomatic at the time of study. Based on our Feeding Outcomes of Dysphagia Study (vs. historical control), the success rate at discharge is around 60%. With 60 patients enrolled, we will have 90% power to detect an absolute increase of 20% from 60% for those who do not have treatment informed by manometry (historical control) to 80% in those in the manometry informed group with two-sided type I error of 0.05. Achievement will be assessed by tracking feeding methods at discharge or 4 weeks whichever is earlier and then at 1 year.
- [name], Peng J, Moore R, Saavedra J, Shepherd E, Fernandez S, Erdman SH, DiLorenzo C. Impact of personalized feeding program in 100 NICU infants: pathophysiology-based approach for better outcomes. *J Pediatr Gastroenterol Nutr.* 2012 Jan;54(1):62-70.
- [name], Stoner E, Gupta A, Bates DG, Fernandez S, Di Lorenzo C, Linscheid T. Evaluation and management of neonatal dysphagia: impact of pharyngoesophageal motility studies and multidisciplinary feeding strategy. *J Pediatr Gastroenterol Nutr.* 2009 Feb;48(2):186-92
- [name], Khot T, Moore R, Malkar M, Gulati IK, Slaughter JL. Feeding Methods at Discharge Predict Long-Term Feeding and Neurodevelopmental Outcomes in Preterm Infants Referred for Gastrostomy Evaluation. *J Pediatr.* 2017 Feb;181:125-130

3.4 Scientific or scholarly background for, rationale for, and significance of the research based on the existing literature and how will it add to existing knowledge

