6.0 Procedures Involved*

6.1 Study Design

- Study design and setting: Eligible subjects (study) will undergo diagnostic VFSS in combination with manometry, either concurrent or sequential. They will have parental choice of preferred feeding therapy. The data is from single center prospective observational study. The controls are those who had VFSS alone with provider recommendations from the same single center.
- Patient population and characteristics: (i) Study and control infants have oral feeding difficulties with symptoms requiring interventions/monitoring. (ii) They have diagnostic need for VFSS due to aerodigestive and feeding difficulties. (iii) Study subjects must have a signed informed consent from parent/legal guardian prior to manometry study. Control subjects did not require consent as they were historical controls.
- Inclusion criteria: Infants with feeding-related aerodigestive symptoms who are \leq 60 wks PMA (both pre-term and full-term) who are orally feeding \geq 25% of at least 50% of their feeds who are on full enteral feeds with no more than 1LPM NC respiratory support. All infants will have a diagnostic VFSS scheduled.
- Exclusion criteria: Genetic or metabolic syndromes, grade III or greater, moderate to severe HIE, craniofacial, airway or foregut malformations or ENT or neuro surgeries. Infants who are exclusively breastfeeding are also excluded.
- Test-1: VFSS with concurrent or sequential pharyngo-esophageal manometry along with standard safety metrics. Esophageal and pharyngeal provocation induced

PROTOCOL TITLE: Neonatal Esophagus and Airway Interactions in Health and Disease: Mechanisms and Management of Infant Dysphagia

aerodigestive reflexes will be tested. Oral feeding challenge test is performed during manometry. The same procedures without VFSS will be repeated at Time-2 where feasible and relevant.

- Overall Study Endpoints: Primary endpoint is therapeutic success defined as full oral feeding without symptoms requiring intervention at 4 weeks (for outpatient studies and those still admitted at 4 weeks) or discharge, whichever is earlier. Secondary clinical end points include growth velocity and feeding outcomes at 1 year.
- Methods to overcome Potential Confounders: It is NICU standard to document in EPIC: i) Daily documentation of symptoms, medication use, feeding methods and duration, feeding volume and weight, ii) Weekly documentation of growth velocity (weight, length, head circumference).

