7.0 Sharing of Results with Subjects*

- 7.1 Manometry results are shared with the parents at the time of the study. Parents decide on their preferred feeding approach (flow change, thickener change, no change) and if the patient is inpatient, this is shared with the medical team.

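### Section 3.3 labels the primary comparison as manometry against no manometry, but 2.2 and 6.1 define a package (manometry plus parent-preferred therapy) against VFSS with provider recommendations

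*Combined protocol and SAP*

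**What the plan says.** The protocol describes the primary contrast in two ways.

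- **As a package.** The primary hypothesis in 2.2 reads: "The addition of manometry for diagnostics and parent preferred therapy for management is more effective than VFSS with provider recommendations alone". Section 6.1 gives study infants VFSS with manometry and lets parents choose the feeding therapy. It says of the comparison group: "The controls are those who had VFSS alone with provider recommendations from the same single center". The central hypothesis, stated in 2.2 and again in 3.4, also joins manometry with parent preference.
- **By manometry alone.** Section 3.3 describes "comparing VFSS and manometry vs VFSS only (the historical control) on feeding outcomes", and sets the target as a rise "from 60% for those who do not have treatment informed by manometry (historical control) to 80% in those in the manometry informed group".

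Sections 1.0 and 5.1 name manometry as the only intervention. Section 1.0 gives its purpose as "in order to determine sensory-motor dysphagic mechanisms which will better inform treatment options". Neither section mentions parent choice as part of what study infants receive.

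Section 7.1 connects the two components. Manometry results are shared with parents when the study is done, and then: "Parents decide on their preferred feeding approach (flow change, thickener change, no change".

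**The concern.** Two things change between the groups: the diagnostic work-up, and who decides on feeding therapy. Section 3.3 names only the first. It is also the section that fixes the success rates, the sample size and the power, so it is where a reader will look to learn what was tested. The revision history says the current version was prepared for clarity and will accompany the manuscript.

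A significant result read through 3.3 would be taken as evidence that manometry raises feeding success. Read through 2.2 and 6.1, it is evidence about the package only. This would be so even if the historical controls were comparable in every other respect. Covariate adjustment cannot help, because no infant has just one of the two components.

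**Working it through.** **Inputs.** From 3.3: 60 study infants, control success 60%, target 80%, "With 60 patients enrolled, we will have 90% power to detect an absolute increase of 20" percentage points, "with two-sided type I error of 0.05". From 6.1: the components each group receives. From 16.1: chi-squared or Fisher tests for categorical comparisons with the historical controls. The number of controls is not given.

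**Step 1. Reproduce the stated power.** Treat 60% as a fixed benchmark.

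- SE under the null = √(0.6 × 0.4 / 60) = 0.0632. SE under the alternative = √(0.8 × 0.2 / 60) = 0.0516.
- Power = Φ[(0.20 − 1.96 × 0.0632) / 0.0516] = Φ(1.47) = 93.0%.
- With continuity correction, subtract 1/(2 × 60) = 0.0083 from the numerator: Φ(1.31) = 90.5%.
- Exact binomial, declaring success at 44 or more of 60: upper-tail error 2.2%, power 92.3%.

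The 90% is reproduced, so the arithmetic is not in question.

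**Step 2. Ask what the 20 points measure.** Write p(diagnostics, decision-maker) for the success rate. There are four possible cells.

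| | Provider recommends | Parent chooses |
|---|---|---|
| VFSS only | observed (controls, 60%) | not observed |
| VFSS + manometry | not observed | observed (study, target 80%) |

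The observed difference splits as

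p(manometry, parent) − p(VFSS, provider) = [p(manometry, parent) − p(VFSS, parent)] + [p(VFSS, parent) − p(VFSS, provider)].

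The first bracket is manometry's effect when parents choose. The second is the effect of changing the decision-maker. Both need p(VFSS, parent), which no group supplies. Splitting through p(manometry, provider) meets the same obstacle. The comparison of flow modification with thickener use in 16.1 contrasts therapies chosen within the study group, so it fills neither empty cell.

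**Step 3. Show what the test responds to.** Assume that manometry has no effect and that parent choice, with any other difference from the controls, adds d points to 60%. Under the exact rule of step 1:

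| d (points) | Success rate | Chance of a significant result |
|---|---|---|
| 0 | 60% | 2.2% |
| 5 | 65% | 11.0% |
| 10 | 70% | 34.2% |
| 15 | 75% | 68.0% |
| 20 | 80% | 92.3% |

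The last row equals the exact power in step 1: the test responds to the total difference, whatever its source. The documents give no value for d, so the table is an illustration and not an estimate.

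**The case against.** The strongest reply is that the governing text already has the contrast right. Section 2.2 states the package, 3.4 repeats it, 6.1 describes both groups accordingly, and 16.1 uses neutral group labels and plans no manometry-only attribution. The sentence in 3.3 even opens by naming the study after preference. All of this stands. It makes the problem a label in 3.3 that contradicts the hypothesis, not a hypothesis that the trial cannot address. A reader might infer that this confounding prevents the trial from addressing its primary hypothesis. It does not, because that hypothesis concerns the package.

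Three other strong readings also go too far.

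- *That 1.0 itself compares manometry with no manometry.* It states no control comparison. It lists manometry in the field for the research intervention, and 5.1 does much the same. Those entries are incomplete, but the mislabelled contrast is in 3.3 only.
- *That parents' choices are not informed by manometry.* Section 7.1 has the results shared with parents, who then decide. No stated rule ties a finding to a choice, and leaving therapy unchanged is an option, but a choice can be informed without such a rule. Part of any manometry effect may act through that choice.
- *That manometry's share lies between 0 and 20 points.* Nothing in the design sets those limits, since parent choice could also lower success. The two components may also not act as separate additive shares. The share is simply not identified.

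That parent choice may carry part of the manometry effect does not restore the 3.3 reading. The decision-maker also moves from provider to parent, and that change comes with every study infant.

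**Conclusion.** The point holds in this form: 3.3 labels the primary comparison and its success rates by manometry alone, while 2.2 and 6.1 define a two-component package. No planned analysis can support a conclusion specific to manometry. The 90% is power to detect a 20-point difference between the package and a fixed 60%, from whatever cause.

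This rests on 6.1's description that all study infants have both components and all controls neither. The figures in the working also treat 60% as fixed, which is the reading that reproduces the stated power. Calendar time and selection by consent are further differences that limit even the package conclusion, but they are separate matters. The remedy leaves enrolment, endpoint, test and sample size as they are; it changes what the trial may conclude.

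**What to change.** 1. In 3.3, replace the comparison and both group labels with the contrast of 2.2 and 6.1: VFSS plus manometry plus parent-preferred therapy, against VFSS plus provider recommendations. State that the 90% refers to this contrast.
2. In the same place, state that the primary result supports a conclusion on the package only, and that no effect will be attributed to manometry alone.
3. In 1.0 and 5.1, keep manometry as the named intervention and add that study infants are managed by parent-preferred therapy.
4. Add one descriptive table of parent choice against the manometry and VFSS findings, showing how often management changed after manometry. Section 2.1 already has therapy changes documented. Include therapy before the study where it is recorded; the daily feeding records described in 6.1 are a NICU standard and may not exist for outpatients. The table describes how manometry was used and does not separate the two effects.

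The cost is a wording change in three sections, one extra table, and a narrower claim for manometry.

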4.0 Study Endpoints

- 4.1 The study endpoint will be independent oral feeding without symptoms requiring intervention by 4 weeks or sooner.
- 4.2 The study will be ended with any safety concerns for the subject

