16.0 Data Management* and Confidentiality

16.1 Data Analysis Plan

- Descriptive statistics will be reported as median (IQR), mean \pm SD or total number and percentage for demographics and clinical characteristics. For PPG vs FOD historical control comparisons, two-sample t-test or ANOVA will be used for the continuous variables and chi-squared or Fischer's exact tests will be used for the categorical variables, whichever is appropriate. Non-parametric method (e.g. Wilcoxon) might be used if the data is not normally distributed. Normality will be assessed using Shapiro-Wilks test and visually inspection of the data. For other Normal vs Abnormal VFSS and the effect of parent preferred therapy -flow modification or thickener use) comparisons, due to the nature of the repeated measure of the data, repeated measure ANOVA for continues measured variables and Generalized estimating equation (GEE) for categorical variables, to predict the likelihood of the specific response, will be used as to make the between group comparisons. Compound symmetry (CS) will be specified for the covariance structure of the repeated data. Bonferroni correction will be used to conserve the overall type I error at $\alpha=0.05$. To characterize the association between the disease comorbidities and feeding success, simple and multiple logistic regression analysis will be performed. Statistical Analysis Software, version 9.4 (SAS Institute Inc., Cary, NC, USA)

- 16.2 Data will be stored in RedCap and each subject will have a file which is kept in a secured locked location.

- 16.3 Data will be verified by at least two individuals on the study team

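### Are the historical controls scored at a different time from the study infants?

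*Combined protocol and SAP*

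**What the plan says.** Three places give the timing rule for study infants, and they agree:

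- Section 2.1 follows feeding progress "till discharge or four weeks, whichever is earlier".
- Section 3.3, last sentence of its first bullet: "Achievement will be assessed by tracking feeding methods at discharge or 4 weeks whichever is earlier and then at 1 year".
- Section 6.1, Overall Study Endpoints, measures therapeutic success "at 4 weeks (for outpatient studies and those still admitted at 4 weeks) or discharge, whichever is earlier".

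Two places are worded differently. Section 3.3 also states that "The primary outcome is success rate at discharge", with no cap in that sentence. Section 4.1 gives the endpoint as "independent oral feeding without symptoms requiring intervention by 4 weeks or sooner".

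For the controls, section 3.3 reports from the FOD study that "the success rate at discharge is around 60" per cent. Section 6.1 describes them: "The controls are those who had VFSS alone with provider recommendations from the same single center". Section 16.1 opens its test plan with "For PPG vs FOD historical control comparisons" and names the tests. Neither 6.1 nor 16.1 attaches a scoring time or a start date to the controls.

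**The concern.** The study has no concurrent comparison arm, so its primary result rests on one binary outcome measured alike in two cohorts. Read literally, study infants are capped at 4 weeks and controls are not. A control infant with a longer stay would then have had more time to reach full oral feeding than a study infant with the same course. Section 6.1 provides for infants still in hospital at 4 weeks, and for outpatients, for whom discharge has no obvious meaning, so such cases are not hypothetical in the study cohort.

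Two further points add to the doubt. Manometry may follow the VFSS rather than coincide with it, and controls had VFSS alone, so a clock started at manometry could not be applied to them. The wording of 4.1 could also be taken as success ever reached within 4 weeks, rather than status on a given day. If the cohorts were scored differently, a difference between them, or the lack of one, could partly reflect timing.

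**Working it through.** **1. The plan's own figure.** Inputs from section 3.3: control rate 0.60, target rate 0.80, n = 60, two-sided α = 0.05 (z = 1.96).

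One-sample normal approximation with continuity correction: power = Φ{[(0.80 − 0.60 − 1/120)·√60 − 1.96·√(0.60·0.40)] / √(0.80·0.20)}
= Φ{(1.485 − 0.960) / 0.400} = Φ(1.31) = 90.5%.

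Exact binomial: the smallest count with upper-tail probability at most 0.025 under 0.60 is 44 of 60 (tail 0.0221). P(X ≥ 44) under 0.80 is 92.3%. The stated 90% therefore holds with 60% taken as a fixed benchmark.

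**2. What the at-discharge label means in this plan.** Section 3.3 uses it twice within a few sentences, first for the study's own primary outcome and then for the FOD rate. The same paragraph closes with the earlier-of rule. So in its first use the label demonstrably names the capped endpoint. Nothing suggests that its second use means something else.

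**3. Whether one outcome covers both groups.** The primary hypothesis in 2.2 compares the two approaches on achieving the primary outcome, in the singular. Section 6.1 describes study and control infants together and then gives a single endpoint definition. The power statement in 3.3 moves from 60% to 80% on one scale.

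**4. The clock.** For study infants it is loosely fixed: section 1.0 ties the 4-week duration to the initial manometry study with diagnostic VFSS, 2.1 counts the repeat study from the initial one, and 8.1 limits participation to 4 weeks. What stays open is the interval between VFSS and a sequential manometry, and the start date for controls. VFSS is the one procedure described for both cohorts, which makes its date the obvious common start.

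**5. Who could be scored differently.** Inpatients discharged before 4 weeks get the same score under either rule. For longer-stay inpatient controls, the gap would be s × c, where s is the share of controls still admitted at 4 weeks and c is the net share of those who reach full oral feeding between then and discharge. The documents give neither s nor c. The gap is zero if either is zero, or if the label is shorthand.

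**6. What a mismatch would cost, by assumption only.** Let q be the true control rate on the study's rule, with n = 60 and exact tests.

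| q (assumed) | Power for q + 20 points, benchmark left at 60% | Power for q + 20 points, benchmark set to q |
|---|---|---|
| 50% | 34.2% | 83.8% |
| 55% | 68.0% | 90.8% |
| 60% | 92.3% | 92.3% |

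With q = 65%, the benchmark left at 60% and no true effect, the chance of a false positive is 11.0% instead of 2.2%. The loss comes from unequal scoring; common scoring costs little power. These values of q illustrate sensitivity and are not estimates.

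**The case for a change.** The strongest case for a change is that implication is not a scoring rule. The FOD outcomes may have been recorded under another protocol's definition, and nothing here says they will be checked against section 6.1. Section 3.2 mentions a complementary protocol on feeding outcomes in dysphagia; that is the natural home for the control definition, but it is not among these documents. The last revision was made for clarity and reproducibility alongside the manuscript, and one sentence would settle the matter.

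The omission stands: the plan does not expressly give the control scoring time or its start date. A sentence saying so would be a courtesy to readers. What does not stand is the step from silence to a difference. Extra time for long-stay controls would tend to work against the study group, so that route would more likely hide an effect than create one. For outpatients the direction is unknown, and no outpatient control is documented. The wording in 4.1 fits the earlier-of rule if sooner is taken to mean discharge; the ever-reached reading is possible but strained beside three consistent statements. Re-abstracting control charts would presuppose a discrepancy that nothing here demonstrates.

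**Conclusion.** This is a gap that analysts fill sensibly, and the plan need not change. Read as a whole, it uses one endpoint for both cohorts: status at the earlier of discharge or 4 weeks, with 4 weeks for outpatients. An analyst would apply that rule to the FOD controls, counting from the VFSS, and the comparison is then made on equal terms. The planning arithmetic is unaffected: 90% is reproduced at 90.5% (corrected normal) and 92.3% (exact).

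No size or direction of bias can be given, because the documents hold no data on control stays beyond 4 weeks or on feeding gains after that point. On the shorthand reading the gap is zero. The conclusion rests on that reading, which the usage in 3.3 supports but does not prove. If the FOD records turned out to follow a different rule, the affected controls (stays beyond 4 weeks and any outpatients) would need scoring on the study's rule before the comparison. That is a check when the data are assembled, and nothing in the plan prevents it.

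### The 90% power in section 3.3 fits a one-sample test against a fixed 60%; the two-sample comparison listed in 16.1 reaches 90% only with about 650 controls, and the control count is never given

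*Combined protocol and SAP*

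**What the plan says.** The sample-size statement is in section 3.3: "With 60 patients enrolled, we will have 90% power to detect an absolute increase of 20% from 60" per cent, "to 80% in those in the manometry informed group", "with two-sided type I error of 0.05". The 60 are the prospectively followed manometry infants; sections 1.0 and 11.1 give the same number. The control rate comes from an earlier study by the investigators, in which "the success rate at discharge is around 60" per cent. No test is named and no number of controls is given, in 3.3 or elsewhere.

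The question being asked is comparative throughout:

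- The primary hypothesis in 2.2 is that manometry with parent-preferred therapy is "more effective than VFSS with provider recommendations alone for achieving primary outcome".
- Section 3.3 describes the design as "comparing VFSS and manometry vs VFSS only (the historical control) on feeding outcomes".
- Section 6.1 makes clear that the controls are individual patients: "The controls are those who had VFSS alone with provider recommendations from the same single center".
- Section 16.1 states: "For PPG vs FOD historical control comparisons, two-sample t-test or ANOVA will be used for the continuous variables and chi-squared" or Fisher's exact tests for categorical variables, whichever is appropriate.

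The primary outcome is a success rate, so it is categorical. Section 16.1 does not assign it a test by name, and no one-sample test against a fixed rate appears anywhere.

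**The concern.** A one-sample test treats 60% as a known constant. A two-sample test treats it as an estimate from a finite group of controls, and that group's sampling error lowers the power. The power in 3.3 matches the first kind of test, whereas 16.1 lists the second. Because the control count is missing, a reader cannot work out what power the primary comparison has.

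The practical risk is in how the result is read. A non-significant finding could be presented as a negative result from a study with 90% power, when the chance of missing a true 20-point gain may be well above 10%. If a one-sample test is used instead, the problem moves to type I error: the comparative hypothesis is then tested as though the control rate carried no uncertainty.

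**Working it through.** **Inputs from the documents.** Study infants n = 60; control rate p0 = 0.60; study rate p1 = 0.80; two-sided α = 0.05, z = 1.960 (all 3.3). Chi-squared or Fisher's exact test (16.1).

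**Assumption.** The number of controls, m, is not in the documents, so a range is shown.

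**Step 1: reproduce the 90%.** One-sample test against a fixed 60%:

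power = Φ{[(p1 − p0) − c − z√(p0(1−p0)/n)] / √(p1(1−p1)/n)}

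with √(0.24/60) = 0.0632, √(0.16/60) = 0.0516 and z × 0.0632 = 0.1240.

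- Continuity correction, c = 1/(2n) = 0.0083: (0.2 − 0.0083 − 0.1240)/0.0516 = 1.311, power 90.5%. The corresponding sample size for 90% power is 59.1, that is 60.
- No correction: (0.2 − 0.1240)/0.0516 = 1.473, power 93.0%.
- Null variance only: 0.2/0.0632 − 1.960 = 1.202, power 88.5%.
- Exact binomial (reject at 44 or more, or 27 or fewer, of 60; size 0.035): 92.3%.

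The stated figure is therefore what a one-sample calculation gives. It does not arise from two groups of 60: the normal approximation there gives 67.0%, and 90% would need 109 per group.

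**Step 2: power of the two-sample tests.** Normal approximation for chi-squared:

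power = Φ{[(p1 − p0) − z√(p̄(1−p̄)(1/n + 1/m))] / √(p1(1−p1)/n + p0(1−p0)/m)}, with p̄ = (n·p1 + m·p0)/(n + m)

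- m = 60: p̄ = 0.700; (0.2 − 1.960 × 0.0837)/0.0816 = 0.441; 67.0%.
- m = 300: p̄ = 0.633; (0.2 − 1.960 × 0.0682)/0.0589 = 1.128; 87.0%.
- m = 650: p̄ = 0.617; (0.2 − 1.960 × 0.0656)/0.0551 = 1.297; 90.3%.

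Full enumeration of both binomials gives the table below (chi-squared without continuity correction, Fisher two-sided). The last two columns give the gain over 60% that is detectable with 90% power.

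| Controls m | Power, chi-squared | Power, Fisher | Detectable, chi-squared | Detectable, Fisher |
|---|---|---|---|---|
| 30 | 52.4% | 46.7% | – | – |
| 60 | 68.4% | 60.0% | 25.5 points | 27.0 points |
| 100 | 76.2% | 74.2% | 23.5 | 23.9 |
| 200 | 84.5% | 82.7% | 21.5 | 21.9 |
| 300 | 87.2% | 85.3% | 20.8 | 21.3 |
| 400 | 88.4% | 87.5% | – | – |
| 650 | 90.1% | 88.0% | – | – |
| 1000 | 90.9% | 89.4% | – | – |

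Chi-squared power moves in small steps. It first touches 90% at 614 controls, is last below it at 676, and is 90.1% at 650; the normal approximation gives 594. Fisher reaches 90% at about 1,300.

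**Step 3: the alternative reading.** Suppose a one-sample test is run against the rate observed in m controls, treated as fixed, and both true rates are 0.60. The two-sided type I error by enumeration (score test / exact binomial) is 16.9% / 14.5% at m = 60, 12.6% / 10.1% at 100, 8.7% / 6.8% at 200, and 7.4% / 5.7% at 300.

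**The case against.** The strongest reply is that nothing has been miscalculated. The protocol calls the study single-arm, enrols 60 infants in one group, and quotes a power that is correct for the usual single-arm calculation against a benchmark. Section 16.1 is a general list of tests that never mentions the primary outcome, so the mismatch is partly inferred. This much stands: the defect is a power basis that does not match the listed analysis, together with a missing test and a missing count, and it is not a slip in the sum. Even so, the two-sample reading is the more natural one, because the hypothesis is comparative, the controls are real patients, and 16.1 offers no other test for a categorical comparison with them.

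Second, the size of the loss depends on an assumed control count. That is true: with 400 or more controls the chi-squared loss is about 2 points or less. The 650 is also approximate (roughly 600 to 675) and depends on the method. An unpooled z test would need only about 211 controls by normal approximation, but it is not one of the tests listed.

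Third, the power loss and the type I inflation are alternatives and cannot both occur. That is correct, and they should not be added together. Each reading still leaves one stated property unsupported.

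Fourth, section 8.1 has enrolment ending in 7/20, so restating the power changes no estimate or interval. That is also true. But the revision history says this version is to accompany the manuscript, so the 90% will shape how the result is read.

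**Conclusion.** The concern holds. As written, the 90% is not the power of the comparison that sections 2.2, 3.3 and 6.1 set up and that 16.1 would analyse, unless there are about 650 or more controls (chi-squared) or about 1,300 (Fisher). If there are 60 to 300, the chance of missing a true gain from 60% to 80% is about 13-32% by chi-squared or 15-40% by Fisher, against the 10% implied.

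This rests on the plan's own 60% and 80%, and on a control range that is assumed because the documents give none. The mismatch and the missing information are certain; the size of the shortfall is not, and could be small if the control group is large.

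**What to change.** In section 3.3:

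1. State the actual number of historical controls.
2. Name one of the two tests in 16.1, chi-squared or Fisher's exact, as the test of the primary outcome, and repeat this in 16.1.
3. Replace the 90% with that test's power for 60 infants against the actual control count, or with the difference it can detect with 90% power.
4. Commit to reporting the risk difference with a two-sample 95% confidence interval.

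If a one-sample test against 60% is what is intended, say so in both 3.3 and 16.1. Add that it tests against a fixed benchmark only, and that it does not hold type I error at 5% for the hypothesis in 2.2 when the 60% is itself estimated from the controls.

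The cost is one paragraph in 3.3, one sentence in 16.1 and a count of existing records. No patients are added and enrolment is unaffected. The stated power will fall unless the control group is very large.
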